The sample size was calculated considering the clinical cure rate of 0.88 submitted to the treatment with PRO-157 1 drop three times a day compared to a percentage of 0.94 of the group with Gatifloxacin. It is expected that at least a healing difference of 15% will be present to demonstrate superiority in the upper and lower limits, in order to demonstrate non-inferiority.

The formula for non-inferiority or superiority was used comparing two proportions¹ with a Power (1-β): 90% and an error type 1, α: 5%. Margin or limit, δ: 15%.

$$n = p(1 - p) \left(\frac{Z_{1-\alpha} + Z_{1-\beta}}{p - p_0 - \delta} \right)^2$$

The result is **112 eyes with acute bacterial conjunctivitis**. Considering an increase of 30% (15) due to the probable losses and a balance between the groups, the final **sample size is 160 eyes**.

The intervention will be applied in both eyes, however each subject will only provide one eye for efficacy analysis.

6.7 Recruitment .

The subjects will be recruited from the IP external consultation or referenced from first level centers. Recruitment will be competitive for all centers.

7. Methods Assignment of the intervention.

7.1 Generation of the allocation sequence.

2 strata corresponding to the intervention groups will be used, which will be balanced for each research center. The allocation will be 1: 1. The generation will be done through an electronic system validated by an external provider, previously evaluated and authorized by Sophia Laboratories S.A. of C.V. The information corresponding to this provider will be found in the master folder of the study.

7.2 Blinding mechanism.

Blinding will be performed by the personnel indicated by the Clinical Operations Management of Sophia Laboratories, S.A. of C.V. The vials of both interventions will be re-labeled and the secondary packaging will be masked.

7.3 Implementation.

The sequence will be generated by means of an electronic randomisation system. Said system will be hired by Sophia Laboratories, S.A. of C.V. to a third party. The information corresponding to this third party will be found in the master folder of the study.

7.4 Blinding and masking.

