To ensure the confidentiality and security of the data, user names and access codes will be used to restrict access to the system only to authorized personnel.

The monitor must ensure that all the data has been filled in the CRF. After comparing the data against the source documents, the monitor will ask the researcher to make the necessary correction / clarification, so that they are answered and closed as quickly as possible.

The Scientific Committee of Sophia Laboratories S.A. of C.V. will give the latest medical-scientific review, and will set the standard for freezing the database.

8.3 Statistical methodology.

8.3.1 Analysis of primary and secondary outcome variables.

The statistical analysis will be carried out by personnel of Sophia Laboratories. The statistical program SPSS version 19 will be used.

The designated personnel will be blinded to the intervention groups. The coding will be done using consecutive numbers for each intervention group.

The data will be collected and sorted in an excel sheet. Later they will be exported to the platform of the SPSS program. The variables will be categorized according to their nature.

The result of the continuous quantitative variables will be presented in measures of central tendency: mean, standard deviation and ranges. See **Table 5 Variable measurement method**. The total size of the samples will consider an eye as a case for the evaluation of efficacy. Paired samples will be considered in cases with visits before and after the intervention.

The normal distribution of results will be obtained through the Kolmogorov-Smirnov and Shapiro-Wilks test, as applicable.

The statistical analysis of the continuous quantitative variables to find significant differences (p) will be the following:

- Inter-group analysis: t test for paired samples.

The level of difference to consider significance will be of an alpha of 0.05 or less.

The result of nominal and ordinal qualitative variables will be presented in frequencies, proportions and percentages. See **Table 5 Method for measuring variables**.

The statistical analysis to identify significant differences of the qualitative variables will be done by creating 2x2 contingency tables and will be done as follows:

- Difference between groups: χ^2 test (Chi-square) of Pearson or Fisher's exact in expected values less than 5.

The level of difference to consider significance will be an alpha of 0.05 or less.

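### No stated rule decides non-inferiority: section 6.6.1 sizes the trial at one-sided 5% against a 15-point margin, but section 8.3.1 names only difference tests at 0.05, with no margin, interval or confidence level

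*Combined protocol and SAP*

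**What the plan says.** **Section 6.6.1 (sample size).** The calculation is made "with a Power (1-β): 90% and an error type 1, α: 5%. Margin or limit, δ: 15" per cent. It assumes a "clinical cure rate of 0.88 submitted to the treatment with PRO-157 1 drop three times a day compared to a percentage of 0.94" for gatifloxacin. The printed formula uses the standard normal quantile at 1 minus alpha, not at 1 minus alpha/2, so it is one-sided, although the text never uses that word. The result is 112 eyes, raised to 160 for 30% losses, or 80 per group. The same section expects that "at least a healing difference of 15% will be present to demonstrate superiority in the upper and lower limits, in order to demonstrate non-inferiority".

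**Section 8.3.1 (analysis).** Clinical remission is a yes/no variable, so it falls under the rule for qualitative variables: "Difference between groups: χ^2 test (Chi-square) of Pearson or Fisher's exact in expected values less than 5". The threshold is: "The level of difference to consider significance will be an alpha of 0.05 or less". Neither the 15-point margin nor a confidence interval, confidence level or sidedness appears.

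**Elsewhere.** The hypotheses in section 5.5.4 carry no margin and no error rate. The statistical paragraph of the summary gives only a t test for continuous variables. No other section supplies the rule.

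**The concern.** A non-inferiority conclusion needs three things fixed in advance: the margin, the error rate with its sidedness, and the interval limit (or equivalent test) compared with the margin. Section 6.6.1 supplies the first two for the sample size. Section 8.3.1 carries neither into the analysis and supplies no third.

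The tests it names ask whether the two remission rates differ. A non-significant result there does not exclude a deficit of 15 points, so the analysis as written cannot deliver the trial's stated conclusion. Someone must add a rule, and the documents leave room for two: the lower limit of a 90% interval, which matches the one-sided 5% of the design, or that of a 95% interval, which matches the usual two-sided reading of 0.05. These carry different error rates and power, and near the planned rates they can disagree on the same data.

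**Working it through.** **Inputs.** From section 6.6.1: p = 0.88 (PRO-157), p0 = 0.94 (gatifloxacin), alpha 5%, power 90%, margin 15 points, losses 30%, 80 per group. Allocation is 1:1 (section 7.1).

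**1. Reproduce the plan's figure.** n = p(1 - p) × [(z_alpha + z_beta)/(p - p0 - δ)]², with p(1 - p) = 0.1056 and z_beta = 1.2816.
- δ = -0.15, so the denominator is 0.88 - 0.94 + 0.15 = 0.09. With z = 1.645 (one-sided 5%), n = 111.65, rounded up to **112**, a match. Then 112/0.70 = **160**, also a match.
- z = 1.960 (one-sided 2.5%) gives 136.99, or 137. No match. After losses, 137/0.70 gives 196.
- δ = +0.15 makes the denominator -0.21 and gives 20.5, or 21. No match.

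The design is therefore one-sided 5% against -15 points, which corresponds to the lower limit of a two-sided 90% interval.

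**2. One data set under the candidate rules.** Take 70/80 on PRO-157 and 75/80 on gatifloxacin, close to the planned rates. The difference is 0.875 - 0.9375 = -6.25 points, with SE = √(0.875×0.125/80 + 0.9375×0.0625/80) = 0.0458.

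| Rule | Result | Reading at -15 points |
|---|---|---|
| 90% lower limit, Wald | -6.25 - 1.645×4.58 = -13.8 | non-inferior |
| 90% lower limit, Newcombe | -14.2 | non-inferior |
| 95% lower limit, Wald | -6.25 - 1.960×4.58 = -15.2 | not shown |
| 95% lower limit, Newcombe | -15.9 | not shown |
| Planned Pearson / Fisher | p = 0.175 / 0.278 | says nothing about the margin |

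**3. How often the two intervals disagree.** Full binomial enumeration at true rates 0.88 and 0.94:
- 80 per arm, Wald: 64.6% pass on the 90% interval and 53.5% on the 95% interval, so 11.0% disagree. Newcombe: 14.9% disagree.
- 56 per arm (80 × 0.70): 11.7% (Wald) and 14.3% (Newcombe) disagree.

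At a true deficit of exactly 15 points (0.79 against 0.94, 80 per arm), non-inferiority is wrongly declared in 5.3% to 6.1% of trials on the 90% interval and 2.6% to 3.2% on the 95% interval.

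**4. Power, and where the shortfall arises.** For two arms, power = Φ(0.09/√[(0.1056 + 0.0564)/n] - z).

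| n per arm | 0.09/SE | one-sided 5% | one-sided 2.5% |
|---|---|---|---|
| 80 | 0.09/0.0450 = 2.00 | 64% | 52% |
| 56 | 0.09/0.0538 = 1.67 | 51% | 39% |

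The printed formula contains the variance of one arm only (0.1056), and its result is then shared between two arms. A two-sample calculation with the same inputs needs 172 per arm at one-sided 5%, or 211 per arm at one-sided 2.5%, before losses. So the fall from 90% to 64% comes from the formula and the resulting 80 per arm. The choice of level accounts only for the further step from 64% to 52%.

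**The case against.** The strongest reply is that the plan contains only one error rate tied to the margin, the one-sided 5% of section 6.6.1, and that 5% appears in both sections. On this view there is no conflict, and the reversal in the example is between two intervals that the plan never mentions. Much of this stands, and it limits the point in four ways.

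- **Two conflicting error rates.** A reader might infer that section 8.3.1 prescribes a two-sided 5% level, hence one-sided 2.5%, for non-inferiority. The documents do not support that. Two-sidedness is only the usual convention for these tests, and the 0.05 is attached to tests of a difference without a margin. The defect is a missing rule, not two competing written ones.
- **An equivalence criterion.** The mention of both limits might be taken for one. The sentence is garbled and mixes superiority with non-inferiority, while the summary, the hypothesis (5.5.4) and the design (5.6) all speak of non-inferiority. It is unclear wording, not another decision rule.
- **The power loss.** Attributing the whole gap from 90% to the level would be wrong, as step 4 of the working shows.
- **A free choice after the data.** Sections 7.4 and 8.3.1 keep the analysts blinded to group, which limits steering. It does not remove it: sponsor staff analyse the data, the sponsor may request further analyses during or after the trial (8.3.2), and it may open the blind for any reason it finds pertinent (7.4.1).

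What does not stand is the suggestion that nothing needs fixing. The one-sided 5% of the design is never carried into the analysis, and the named tests cannot use it.

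**Conclusion.** The point holds as a missing decision rule. Followed as written, section 8.3.1 cannot show non-inferiority at any alpha, because neither the margin nor an interval enters it. If a rule is added without a level fixed in advance, the two natural candidates disagree in about 11% to 15% of trials at the planned rates with 80 per arm. The stated 90% power is not delivered under either: about 64% or 52% at 80 per arm, and 51% or 39% with 56 evaluable per arm.

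These figures assume true remission rates of 0.88 and 0.94, independent arms of equal size, one eye per subject, and the normal approximation for power. The 56 assumes that the full 30% loss occurs. The documents do not show that one-sided 2.5% is the correct level; preferring it to the design's own 5% is a choice, not a correction.

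**What to change.** **Section 8.3.1, before database lock.** State that PRO-157 is non-inferior if the lower limit of one named confidence interval for the difference in day-8 remission (PRO-157 minus gatifloxacin) lies above -15 percentage points. Name the level and the interval method, since Wald and Newcombe limits differ. The 90% interval is consistent with the existing one-sided 5% design; the 95% interval (one-sided 2.5%) is the stricter option.

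**Section 6.6.1.** Label alpha as one-sided at that same level, write the margin as -15 points, and delete the clause about superiority in both limits. Replace the stated 90% power with what 80 per arm gives: about 64% at one-sided 5% or 52% at one-sided 2.5% (51% or 39% with 56 evaluable per arm).

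**Cost.** A few sentences and a less favourable stated power; no change to procedures. If 160 eyes are kept, no more patients are needed, but the lower power has to be accepted openly. Choosing one-sided 2.5% would raise even the plan's own formula from 112 to 137 eyes, or from 160 to 196 after losses, and that formula already understates what two arms need.

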6.5.2.4 Final Visit

- Pregnancy test: see 6.5.2.1 Baseline visit.
- Conjunctival secretion sampling: see section 6.4.3.4 Conjunctival secretion sampling for bacterial culture
- Ophthalmological examination: see 6.5.2.1 Baseline visit.
- Biomicroscopy: see 6.4.3.1 Biomicroscopy
- Global qualification of the researcher: see 6.4.3.2 Global qualification of the researcher
- Evaluation of concomitant medications: see 6.5.2.1 Baseline visit.
- Assessment of adverse events: see 6.4.3.3 Evaluation of adverse events
- Continuity evaluation: see 6.5.2.2 Visit 1
- Adherence evaluation: see 6.5.2.2 Visit 1
- Global qualification of the researcher: see 6.4.3.2 Global qualification of the researcher
- Return of the medication: refers to the delivery, by the subject, of the excess medication to the research center.
- Return of the subject's diary: refers to the delivery, by the subject, of the tool "subject's diary" to the research center.

6.5.2.5 Security call:

- Assessment of adverse events: see 6.4.3.3 Evaluation of adverse events.

6.5.3 Diagram of the study.

[figure not shown]

Figure 6. Diagram of the study.

6.6 Sample size.

The sample size calculated for the present study is 160 eyes. They plan to recruit 160 subjects, each one will provide an eye for the study, for the analysis of efficacy.

Divided into two intervention groups, each group will be comprised of 80 eyes.

6.6.1 Calculation of the sample size.

The sample size was calculated using the formula for variables of two proportions, likewise the data was entered into the online calculator, software developed in: www.powerandsamplesize.com based on Chow S et al. [39]

Based on the final report of the Phase II clinical study, and the difference found between the intervention of PRO-157, three times a day, against gatifloxacin 0.3%, the calculation of the sample size was made.

The dosage that showed the greatest efficacy was the instillation of 1 drop three times a day. A cure percentage of 88% was observed with the mentioned group. The group that received Gatifloxacin reported a cure rate of 94%. Nevertheless, there was no statistical difference between the groups. [35]

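### The 112 eyes come from a one-sample formula but are split over two arms, so at 88% vs 94% power is about 64% (80 per arm) or 51% (after the full 30% losses), not 90%

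*Combined protocol and SAP*

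**What the plan says.** Section 6.6.1 names the method twice: "The sample size was calculated using the formula for variables of two proportions", and later "The formula for non-inferiority or superiority was used comparing two proportions". The inputs come from the phase II report: "considering the clinical cure rate of 0.88 submitted to the treatment with PRO-157" three times a day, against "a percentage of 0.94 of the group with Gatifloxacin". The section adds type 1 error 5%, "Power (1-β): 90"% and "Margin or limit, δ: 15"%.

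The formula it prints is n = p(1 - p) × [(Z(1-α) + Z(1-β)) / (p - p0 - δ)]². The stated result is "112 eyes with acute bacterial conjunctivitis". An allowance of 30% for losses, and for balance between groups, brings this to 160. Section 6.6 then fixes the split: "Divided into two intervention groups, each group will be comprised of 80 eyes". Section 7.1 gives 1:1 allocation. The Summary repeats 160 patients and 80 eyes per group.

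**The concern.** The printed formula does not match the method named in the text. It has p(1 - p) for one group only, and p0 enters as a constant with no variance of its own. That is the calculation for one sample against a known rate. A randomised comparison must also carry the sampling variance of the gatifloxacin arm.

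A second step adds to the problem. In a one-sample formula, n is the number of treated eyes, here PRO-157 eyes. The plan takes that n as the total for both arms, so the control variance is left out and the PRO-157 arm is also halved.

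The 90% figure is the only power justification for enrolling 160 patients. If it is wrong under the plan's own assumptions, the sponsor and the ethics committees are relying on a chance of success that the design does not have.

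**Working it through.** **Inputs (section 6.6.1 unless noted).** PRO-157 rate 0.88; gatifloxacin rate 0.94; margin 15 points; α = 5%, one-sided because the formula uses Z(1-α); power 90%; losses 30%; 80 per arm (section 6.6). z(0.95) = 1.645, z(0.90) = 1.282, and the square of their sum is 8.564 (from unrounded z).

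**1. Reproducing the plan's figure.** Take the printed formula with δ = -0.15:

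- Denominator: 0.88 - 0.94 + 0.15 = 0.09, squared 0.0081
- Variance: 0.88 × 0.12 = 0.1056
- n = 0.1056 × 8.564 / 0.0081 = 111.65, so 112
- 112 / 0.7 = 160

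Both stated figures match exactly. With δ = +0.15, as the margin is printed, the denominator is -0.21 and n = 0.1056 × 8.564 / 0.0441 = 20.5, so 21. The 112 therefore depends on a sign convention that the section does not state.

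**2. Could another method have given 112?** At the stated rates, the two-sample forms give 172 per arm (unpooled variance), 174 (pooled) or 211 (one-sided 2.5%). The one-sample form at 2.5% gives 137, and with the rates swapped it gives 60. Assuming no true difference gives 43 to 81 per arm. None of these is 112, per arm or in total.

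**3. Two-sample requirement for the same inputs.** The variance sum is 0.88 × 0.12 + 0.94 × 0.06 = 0.1056 + 0.0564 = 0.1620.

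n per arm = 0.1620 × 8.564 / 0.0081 = 171.3, so 172. That is 344 evaluable in total. Allowing for 30% losses, 172/0.7 gives 246 per arm, 492 in total.

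**4. Power of the planned design.** Power = Φ(0.09 / √(0.1620/n) - z(1-α)), with n evaluable per arm.

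| Evaluable per arm | 0.09 / SE | Power, one-sided 5% | Power, one-sided 2.5% |
|---|---|---|---|
| 80 (no losses) | 2.000 | 63.9% | 51.6% |
| 56 (112/2, full 30% losses) | 1.673 | 51.1% | 38.7% |
| 112 (if 112 had been meant per arm) | 2.366 | 76.5% | 65.8% |

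Exact binomial power of the same confidence-limit test at one-sided 5% is 64.6% (80 per arm) and 51.6% (56 per arm), so the normal approximation does not drive the result.

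**5. Where about 90% would be reached (same formula, 15-point margin, one-sided 5%).** The answer depends on both arms' rates.

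| True PRO-157 | True gatifloxacin | Evaluable per arm | Power |
|---|---|---|---|
| 91% | 94% | 80 | 89.3% |
| 93% | 94% | 56 | 91.3% |
| 88% | 88% | 80 | 89.9% |
| 92% | 92% | 56 | 90.0% |

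**The case against.** Nothing elsewhere in the protocol repairs the calculation, and the exact match rules out a printing slip. The best objections concern how far the conclusion reaches.

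- **The result is conditional.** A reader might infer that the trial has 51% to 64% power whatever the truth. The documents do not support that: the range belongs to a true 6-point deficit. With 88% in both arms, 80 per arm already gives about 90%. This stands, and the conclusion has to carry its conditions.
- **PRO-157's rate alone does not decide it.** A reader might also infer that 90% power requires a true PRO-157 rate of 91% to 93%. That holds only with gatifloxacin fixed at 94%, as the last table shows.
- **The loss allowance can be read in other ways.** The 56 per arm is inferred from 112/2 and is not printed. The sentence on losses also mentions balance between groups and carries an unexplained 15 in brackets. Dividing 160 by 1.3 leaves about 123 evaluable, or 61 per arm and 54% power. Reading the 15 as 15% losses leaves 68 per arm and 58%. So 51% is the least favourable of these readings. It is still a real scenario: section 6.3.2 limits the efficacy analysis to at least 80% adherence, section 8.3.3 requires baseline and final measurements, and section 8.3.1 rules out replacement. Section 8.3.3 also promises an intention-to-treat analysis. With complete outcomes, 80 per arm and 64% apply there.
- **The test is assumed.** Section 8.3.1 names only Pearson's chi-square or Fisher's exact test at 0.05, with no non-inferiority interval and no sidedness. The powers here are for a confidence-limit test against the margin, which is what the sample-size formula presupposes. They are not the power of a chi-square test of difference.

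None of these points restores 90% at 88% vs 94%. Even 112 evaluable per arm would give 76.5%.

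**Conclusion.** The point holds, with conditions. Section 6.6.1 claims a two-proportion method but uses a one-sample formula, and then spends the one-sample n on two arms. For true rates of 88% and 94%, a 15-point margin and a non-inferiority confidence-limit test at one-sided 5%, power lies between about 51% (full 30% loss) and 64% (no loss), against the stated 90%. One-sided 5% follows from the printed Z(1-α) and is the more favourable choice. The evaluable number needed for 90% at those rates, 344, is about three times the 112 planned (344/112 = 3.07).

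This is an error in the stated power. It does not show that the trial will fail, since power is higher if the true difference is smaller than 6 points. Nor does it by itself settle that the trial must be enlarged.

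**What to change.** In section 6.6.1:

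1. Replace the formula with n per arm = [pT(1 - pT) + pC(1 - pC)] × [(zα + zβ) / (pT - pC + 0.15)]², where T is PRO-157 and C is gatifloxacin. State the sign convention (δ = -0.15).
2. Delete the 90% power claim for 88% vs 94%.
3. State that at those rates, with the 15-point margin and a confidence-limit test at one-sided 5%, 160 randomised eyes give about 64% power with no losses and about 51% if the full 30% is lost (56 per arm). If one-sided 2.5% is intended, give about 52% and 39%.
4. If a 90% scenario is quoted, give both arms' rates. With gatifloxacin at 94%, about 90% needs a true PRO-157 rate of about 91% (80 per arm) or 93% (56 per arm). With equal rates, 88% in both arms gives about 90% at 80 per arm, and 92% in both arms gives about 90% at 56 per arm.
5. Note that 90% at 88% vs 94% would need 172 evaluable per arm.

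If the size is kept, the cost is the rewording of one section and a less favourable stated power; no procedure changes. Enlarging the trial is a separate decision for the sponsor.

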- III. History Users of contact lenses who are not willing to suspend their use during the study.
- IV. Users of any formulation with ophthalmic application, including lubricants, that can not, or do not want to suspend it during the study.
- V. Antecedents of eye surgery 6 weeks prior to study entry.
- VI. Viral or allergic conjunctivitis.
- VII. Active uveitis.
- VIII. Active ulcerative keratitis.
- IX. Recurrent corneal erosion syndrome
- X. Antecedent of hypersensitivity or allergy to fluoroquinolones.

6.2.3 Elimination criteria.

- I. Subject's decision. The subject may decide unilaterally to withdraw from the study at any time.
- II. Pregnancy.
- III. Presence of a serious adverse event (EAS), including the presence of hypersensitivity.
- IV. Investigator's decision:
 - a. Due to the presence of an EA that, although not serious, at the discretion of the IP merits the prescription of a medicine not authorized in the protocol.

V. Any deviation to the protocol that affects the security of the subject.

6.2.4 Identification of the subject.

The patients of the study will be identified by a number and the initials of their name.

The initials of the study subject will be obtained by starting with the first letter of the name, followed by the first letter of the first surname and the first of the second, obtaining maximum three letters, in case the person has two names or a compound surname will always be used the first letter of the first name or last name composed.

Example:

1. Adolfo Daniel Mercado Carrizales

a. a. Initials: AMC

2. Juan De la Torre Orozco

a. Initials: JDO

[figure not shown]
3. Luis Carlos Pérez-Gómez Ramírez

a. Initials LPR

In the counting stage, the participant number will be assigned consecutively, using 3 consecutive digits. Once the subject has been selected, he will be assigned a number with which he will be identified throughout the study. Said code will be composed of eight numbers in the following order from left to right:

- Three digits of the molecule under study according to the denomination by the sponsor.
- Two digits corresponding to the research center number
- Three digits of the number consecutive to its inclusion assigned in the research center.

Example:

6.3 Intervention.

6.3.1 Managed treatments.

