Once all discrepancies generated by the team of clinical monitors and clinical staff have been resolved, the data will be downloaded into an electronic database (Excel Sheet) by personnel designated by the sponsor. A new review of the data will be carried out to corroborate the fidelity of the same and new discrepancies may be generated in case it was considered.

The database generated will be safeguarded by the sponsor and will only have personal access designated by the same.

8.1.1 Strategies to complete the follow-up.

- You will be clearly informed of the importance of the study and the benefits that the population will obtain from the results of the study.
- Transportation assistance will be provided in order for the participant to attend their visits.
- A printed calendar will be provided with the objective of reminding the participant of their appointments and the activities that will be carried out, in addition to the estimated duration of the same.
- In case the participant does not attend his appointment, the research center must make a call to know the reason and try to arrange a new appointment within the established window period or an unscheduled appointment.
- In case it is not possible to make an appointment, it will be asked about the presence of adverse events and the reason for leaving the study, such as minimum data.

8.2 Data management.

The subject's medical record (including clinical notes, test results, etc.), as well as the subject's diary, are considered source data.

The IP or the designated person of your team will fill out the Case Report Format (CRF) as well as all other documents provided by the sponsor (for example: documents related to the management of the treatment).

An electronic CRF was designed to record the data that are required in the protocol and that the researcher collects in each of the visits.

In the case of self-assessment questionnaires, it is not permissible for the principal investigator or person responsible for filling in to modify what was written by the subject of the study.

The data capture in the investigator's site will be done by the investigator or the designated person of his team after performing the Medical File. The researcher or a designated person of your team will be trained in filling the CRF.

All corrections to the CRF data should be made by the investigator or the designated person of your team in accordance with the instructions provided.

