For the reporting of adverse events all participating subjects who were randomly assigned to an intervention group will be considered. The results will be expressed in number of subjects.

The final report of the results will be shown in tables or graphs, as appropriate.

In case of loss of cases (data), they will not be replaced by any situation to complete the sample size.

According to the data obtained, the sponsor will decide to perform a subanalysis by age groups, which will have no influence on the final result.

8.3.2 Additional analyzes.

An internal analysis will be made to know the changes that occur between each visit. It is the sponsor's prerogative to request an additional analysis of the data, during the conduction of the study or at the end of this.

8.3.3 Population analysis and management of missing data.

The effectiveness analysis will consider those cases in which the measurements of the baseline and final visit are met. Those subjects who do not comply with any of these measurements will not be integrated into the final database to evaluate the effectiveness. Nevertheless, an intention to treat analysis (ITT) will be carried out.

The safety assessment will include in the analysis all those subjects (considering one eye or both) who have been exposed at least once to any of the interventions regardless of the visit in which they were eliminated from the study.

9. Methods Monitoring.

9.1 Data monitoring.

Monitoring visits by a site monitor from Sophia Laboratories, S.A. of C.V. are intended to confirm that the studies sponsored by Sophia Laboratories, S.A. of C.V. they are conducted in accordance with the ethical principles that have their origin in the Declaration of Helsinki and that are consistent with Good Clinical Practices and with the applicable regulatory requirements (verifying a continuous compliance with the protocol, amendment or amendments, reviewing accounting records of the product under investigation, verifying that the personnel of the site and the facilities remain adequate to carry out the study).

The researcher must ensure that they have sufficient time, space and qualified personnel for the monitoring visits.

In order to carry out the monitoring review, it is mandatory to provide direct access to all source data and those related to the study site. The monitor will conduct a review of the CRF and a

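### Participants eliminated or lost before day 8 need not be graded, and elimination can follow treatment failure, so failures can drop out of the efficacy comparison and the promised ITT lacks their outcomes

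*Combined protocol and SAP*

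**What the plan says.** The primary endpoint is clinical remission on day 8, recorded as 'Yes' only when hyperemia and secretion are both graded 0 at the slit lamp (6.4.2.1, 6.4.3.1). Both signs and remission status are also recorded at visit 1, on day 5 ± 1 (6.4.4, 6.5).

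After a missed visit, section 8.1.1 has the centre telephone and try to rebook, inside the window or as an unscheduled appointment. If that fails, "it will be asked about the presence of adverse events and the reason for leaving the study, such as minimum data". The day-15 security call covers adverse events (6.5.2.5).

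Section 6.2.3 lists the grounds for elimination. One is an adverse event that is not serious but, in the investigator's view, "merits the prescription of a medicine not authorized in the protocol". It does not say whether an eliminated participant returns for the day-8 grading. Section 9.3.1.1 requires lack of therapeutic response to be reported as an adverse reaction.

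Section 8.3.3 restricts the efficacy analysis to cases with baseline and final measurements, then adds: "Nevertheless, an intention to treat analysis (ITT) will be carried out". It gives no ITT definition and no rule for missing outcomes. Lost cases are not replaced (8.3.1). On sample size, section 6.6.1 reads "Considering an increase of 30% (15) due to the probable losses", and gives balance between groups as a second reason for the increase.

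**The concern.** Read together, these sections let the outcome decide who is analysed. An eye that does not respond can be reported as an adverse reaction. If it is judged to need a medicine the protocol does not authorise, the participant may be eliminated. No final grade is then required, and without one the participant is outside the efficacy analysis.

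The arm with more failures loses more of them this way, even if the same share of failures is eliminated in each arm. The completers' difference moves toward zero, which in a non-inferiority trial favours the claim. The ITT should be the safeguard, but the day-8 outcomes it needs have not been collected. A missing-data rule can be written later. Day-8 eye status cannot be recovered later in a condition that section 5.1.3 describes as self-limiting in at least 60% of cases.

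**Working it through.** **Inputs.** From 6.6.1: remission 0.88 (PRO-157) and 0.94 (gatifloxacin), margin 15 points, α 5%, power 90%, 30% allowance. From 6.6: 80 eyes per group. The level is taken as one-sided because the printed formula uses Z(1-α). The plan names no confidence interval, so two were used (Newcombe and Wald).

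**The plan's own figures.** n = 0.88 × 0.12 × (1.645 + 1.282)² / (0.88 - 0.94 + 0.15)² = 111.6, so 112. Then 112 / 0.7 = 160. Both reproduce. (Whether a one-sample formula suits a two-arm trial is a separate question.) The allowance is therefore at most 0.30 × 160 = 48 eyes, 24 per arm.

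**Case A: losses that depend on outcome (assumed).** Set the truth at the margin: gatifloxacin 0.94, PRO-157 0.94 - 0.15 = 0.79. Let 25% of failures in each arm be eliminated ungraded.

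- Eyes lost: 0.25 × 0.21 × 80 = 4.2 on PRO-157 and 0.25 × 0.06 × 80 = 1.2 on gatifloxacin, about 5 of 160.
- Completers' remission, PRO-157: 0.79 / (0.79 + 0.75 × 0.21) = 0.834.
- Completers' remission, gatifloxacin: 0.94 / (0.94 + 0.75 × 0.06) = 0.954.
- Apparent deficit: 12.1 points instead of 15.

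Summing the binomial probabilities of every result whose lower limit lies above -15 points gives these false non-inferiority rates:

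| Share of failures eliminated (assumed) | Completers' deficit | Newcombe | Wald |
|---|---|---|---|
| 0 | 15.0 | 5.3% | 6.1% |
| 10% | 13.9 | 7.8% | 9.1% |
| 25% | 12.1 | 14.4% | 17.2% |

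**Case B: losses unrelated to outcome.** With 30% lost and 56 completers per arm at 79% v 94%, the completers analysis gives 5.0% (Newcombe) and 6.0% (Wald), so there is no inflation. If the ITT scored every missing eye as a failure, the rates would become 0.79 × 0.7 = 0.553 and 0.94 × 0.7 = 0.658. The deficit is then 10.5 points and the false claim rate 15.5% / 14.1%.

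**Reading A and B together.** In case A the missing eyes are failures, so the completers analysis misleads and scoring them as failures is right. In case B the completers analysis is sound and scoring as failure misleads. Without outcome information on the lost eyes, the data cannot show which case applies.

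**How far the choice of rule can move the result.** Take the plan's 0.94 and 0.88 in completers and equal losses per arm. The worst case counts missing PRO-157 eyes as failures and missing gatifloxacin eyes as successes; the best case reverses this. At an assumed 5% loss the difference runs from -10.7 to -0.7 points. At 10% it runs from 0.88 × 0.9 - (0.94 × 0.9 + 0.10) = -15.4 to +4.6. At the full 30% it runs from -34.2 to +25.8. A 10% loss is enough for the worst case to cross the margin.

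**The case against.** The strongest reply is that the plan does more than the quoted sentence suggests. Rebooking comes first and could yield a grade. The listed items are a minimum, not a limit. The adverse-event question can bring out treatment failure, since lack of response is reportable, and therapy given for the event is recorded under concomitant medications (9.3.1.1). The investigator follows adverse events to their end (9.3.1.2). Participants who attended visit 1 have a day-5 status.

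All of this stands, and it rules out several stronger readings:

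- **That the ITT has no outcome data for 30% of participants.** The 30% also covers group balance. Participants below 80% adherence leave the efficacy analysis (6.3.2) but may have day-8 grades. Forty-eight missing outcomes is an upper bound, not a forecast.
- **That the plan itself raises the error rate to about 15%.** The 14-16% figure needs missing scored as failure, a rule the plan never states.
- **That the ITT must impute.** It needs a stated missing-data rule; which one is open.
- **That eliminated participants are barred from the day-8 visit.** Section 6.2.3 is silent; it neither requires nor forbids the visit.
- **That telephone answers can replace the lost grades.** Remission needs slit-lamp grades of 0, which a call cannot supply.

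The reply does not close the gap. No text obliges a site to obtain or ask about day-8 signs once rebooking fails. A day-5 status is not the endpoint, and no rule says whether it may be used. A recorded adverse reaction still leaves the participant without a final measurement, and so outside the efficacy analysis in 8.3.3.

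**Conclusion.** The concern holds as a gap in outcome collection linked to elimination. Failures can leave the efficacy comparison ungraded, and the promised ITT has neither their outcomes nor a rule for them. In the illustration, about 5 ungraded failures out of 160 eyes reduce a true 15-point deficit to about 12 and raise the false non-inferiority rate from 5-6% to about 14-17%.

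That size rests on assumptions: a true difference at the margin, a one-sided 5% level, and 25% of failures eliminated in each arm. The documents give no elimination rate; at 10% the error rate is about 8-9%. If losses are unrelated to outcome, the completers analysis is not inflated. The change is cheap and should be made before enrolment.

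**What to change.** 1. **Section 6.2.3:** state that elimination does not end follow-up, and that the participant is still invited to the day 8 (+1) grading unless consent is withdrawn. Use that grade in the ITT.
2. **Section 8.1.1:** add to the minimum data whether secretion or redness persists in the study eye, and whether any other anti-infective or anti-inflammatory was used.
3. **Section 8.3.3:** define the ITT population. Count reported persistence or other anti-infective treatment as 'No'. Do not count a telephone report of a clear eye as graded remission. Show the remaining unknowns under best-case and worst-case assignment by arm. State in advance which rule governs when a participant has both a day-8 grade and another anti-infective.

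The cost is one sentence in 6.2.3, two questions in a call already made, a short paragraph in 8.3.3, and some effort to bring eliminated participants to a visit already scheduled. The limitation is that telephone reports confirm failure better than remission, so the return visit is the more valuable part. None of this alters treatment or the grounds for elimination.
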